Other alcohol expectancies may also be relevant. Positive alcohol expectancies (e.g., mood enhancement, tension reduction) may impel or inhibit suicidal behavior, depending on one's mood state. For example, individuals who are depressed may hold the belief that AUA will improve their mood; however, distress often *increases* when alcohol is consumed during negative mood states^{12,13}, potentially increasing risk for suicidal thoughts and behavior.² In contrast, individuals with such expectancies who experience positive mood prior to drinking are likely to experience increases in positive mood, and thus reduced likelihood of suicidal thoughts and behaviors. My preliminary work has partially supported this idea, showing that problematic drinking was negatively associated with suicidal ideation among those with high positive alcohol expectancies.⁹ Albeit limited, the literature suggests an interactive effect among AUA, mood, and alcohol expectancies on suicide risk but there remains a need to test the main effects of alcohol expectancies on suicide-related attentional bias.

The Proposed Study

This pilot experiment will examine the interactive impact of AUA, mood, and alcohol expectancies on suicide-related attentional bias (See Figure 1). This study is an innovative and robust exploration of theory-guided hypotheses. It will employ an experimental design (rare in the study of suicide-related constructs), alcohol administration, mood induction, and performance-based measure of suicide-related attentional bias. This study will 1) demonstrate feasibility of procedures, 2)

[figure not shown]

Figure 1. Hypotheses guided by theory and preliminary studies

explore sociodemographic differences in feasibility an of procedures and in suicide-related attentional bias, and explore conditional effects of AUA on suicide-related attentional bias by 3) mood states and 4) alcohol expectancies.

Innovation

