Session 2. Participants who remain eligible will be scheduled for a second appointment, which will be one to ten hours in duration, depending on their randomly-assigned condition (i.e., alcohol vs. placebo). When scheduling Session 2, participants will be told to refrain from drinking alcohol or using recreational drugs 24 hours prior to the session and to refrain from eating four hours prior to the session. Upon arrival at the laboratory, eligibility will be confirmed, including a breathalyzer test to ensure a zero BrAC and field sobriety test for comparison post-detoxification. Those with nonzero BrAC will be rescheduled. Female participants will be given a pregnancy test kit and asked to produce a urine sample in a private bathroom located adjacent to

the laboratory (those with positive tests will be excluded). Height and weight will be measured to calculate alcohol dosage. We will assess pre-manipulation mood via the Positive and Negative Affect Schedule-Expanded Form (PANAS-X)–sadness, guilt, and joviality subscales³⁸ and 2-item Brief Hopelessness Measure.³⁹

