Manipulation of AUA and Mood: We will randomly assign eligible participants to conditions using a randomization scheme. They will proceed first to beverage administration. We will tell all participants that they are drinking alcohol. Participants in the placebo control group will receive beverages containing 4 mls of alcohol in juice and 4 mls layered on top of the juice. In addition, the rims of the glasses will be sprayed with alcohol just prior to being served. Participants in the alcohol condition will be administered two drinks consisting of an overall dose of 0.99 g/kg (males) or .90 g/kg (females) body weight of 95% ethanol USP mixed in a 1:5 ratio with Tropicana orange juice. Standard drink equivalents will be based on body weight. The beverage will be poured into two glasses in equal guantities. This dose has been used in past studies of alcohol-related self-aggression and reliably produced BrAC levels between .08%-.10%, which is within NIAAA safety guidelines.⁴⁰ This dose has consistently potentiated self-aggressive behavior⁵ and thus was chosen to maximize the likelihood of producing an alcohol-related effect on suicide-related attentional bias. We will serve all beverages chilled with no ice. We will allot twenty minutes for beverage consumption. Participants will be given their two glasses at equally-spaced times to control drinking rate. Immediately after consumption, all participants will rinse their mouths with water. We will assess BrACs of all participants with an Alco-Sensor IV breath analyzer every five minutes for 20 minutes for placebo participants and until .08% on the ascending limb of the BrAC curve for alcohol participants.

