Upon reaching a BrAC of at least .075%, a brief manipulation check will be performed. Participants will rate their level of intoxication on a scale of 0 (0=not at all) to 11 (11=more drunk than I have ever been).⁴¹ Immediately after, participants will be randomized to a 10-minute mood induction procedure. A self-referent plus musical mood induction paradigm will be employed to induce a positive or negative mood state in participants.⁴² Self-referent statements (e.g., negative or positive self-statements) and musical mood inductions are both valid, stand-alone procedures for inducing mood. The combination of both has been shown to be effective in inducing a temporary negative mood state in 75% of subjects.⁴² The combined negative mood induction paradigm was created based on a modernized version⁴³ of a seminal, self-referent mood induction⁴⁴ and a musical mood induction.⁴⁵ Participants will read 25 statements presented in a timed, PowerPoint slideshow, first to themselves and then aloud, and are instructed to "feel and experience each statement as it would apply to you personally." They will concentrate on each statement for 20 seconds and then proceed to the next one. Five statements were revised to generalize to the greater population. This is done simultaneously with the musical negative mood induction paradiam, which involves listening to a piece of music that conveys a particular mood (negative: Prokofiev's 'Russia Under the Mongolian Yoke' at half speed; positive: Delibes 'Coppelia'). These musical pieces were chosen as they are the most studied of the effective musical induction procedures.⁴⁶ Subjects will be left alone in the room during the mood induction to lessen inhibitions but will be observed by way of a window.

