Manipulation Check and Dependent Variable Measurement: After the mood induction, participants will complete the PANAS-X subscales as a manipulation check (<2 min). Participants will then complete a Stroop⁴⁷ task modified to assess attention towards suicide-related cues (i.e., Suicide Stroop³). This modified Stroop task is a performance-based measure conducted via computer that documents response latencies on identification of the colors of words presented on the screen. Neutral (museum, paper, engine), negative (alone, rejected, stupid), positive (happy, success, pleasure), and suicide-related (suicide, dead, funeral) categories of words are presented, and greater response latencies indicate greater interference of the semantic content in naming the color. Participants will be instructed to indicate the word color as guickly and accurately as possible using red and blue keys. Stimuli will be presented using Empirisoft DirectRT software.⁴⁸ Trials will be presented in a random order to each participant. Interference for suicide-related words (i.e., suicide-related attentional bias) will be calculated by subtracting the response latencies for neutral words from the latencies for suicide-related words.³ Internal consistency coefficients for reaction time tasks like Stroop tasks are typically low⁴⁹⁻⁵⁰, and it has been suggested that using internal consistencies from past studies is inadvisable as sample characteristics can have a significant impact on the internal consistency.⁴⁹ Nonetheless, in our partial test, the internal consistencies for the interference scores (using a split-half coefficient) and the suicide trial reaction times were .49 and .86, respectively, which are typical of Stroop tasks⁵⁰⁻⁵¹ and much better than reliabilities in prior studies using the Suicide Stroop.²⁸ The Suicide Stroop has demonstrated construct validity through associations with past and future suicidal behavior.^{3,21} Thus. It serves as the primary outcome

of interest. Following the Stroop, participants will complete the 2-item Brief Hopelessness Measure³⁹ (a secondary outcome, see *Potential Problems* below).

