Pre-Manipulation Mood and Cognition (PANAS-X; Brief Hopelessness Measure)
Manipulation Procedures and Checks
Alcohol or placebo administration; Post drinking BrAC measurement; Manipulation check
Mood induction (positive or negative); Manipulation check: PANAS-X
Outcome Measure: Modified Stroop-Suicide (primary outcome of interest), Brief Hopelessness Measure
Post-Study Procedures: Detoxification (if applicable); Post-Study Verbal Interview, Paykel Suicide Scale
(current; risk screening for post study interview), Debriefing, Payment
Follow up Wollness Check Dhone Calle (day of day following, and wook following)

Follow-up Wellness Check Phone Calls (day of, day following, and week following)

Analytic plan

H1: We will quantify the number of individuals screened and the percentage who are eligible and participate. We will run descriptive statistics to quantify 1) prevalence of successful mood induction, 2) distress ratings post-study session, and 3) number of adverse events. Using measures of effect size, t-tests, and Chi square analyses, we will examine sociodemographic differences in these feasibility factors. H2: We will use measures of effect size, t-tests, and Chi Square analyses to examine sociodemographic differences in suicide-related attentional bias scores. H3: The interactive effect of mood and AUA on suicide-related attentional bias will estimated model be using а general linear of the form $\hat{Y} = \beta_0 + \beta_1 Alcohol + \beta_2 Mood + \beta_3 Alcohol \times Mood$. **H4:** The interactive effect of alcohol expectancies and AUA on suicide-related attentional bias will be estimated using a general linear model of the form $\hat{Y} = \beta_0 + \beta_1 Alcohol + \beta_2 Expectancies + \beta_3 Alcohol \times Expectancies$. For H3 and H4, we will use linear contrasts to estimate effects. Inferences will be conducted using 68% CIs for comparisons of interest, as significance testing is not a primary study aim. See Statistical Design and Power attachment.

Potential Problems, Alternative Strategies, Benchmarks for Success, and Impact

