COVER PAGE

Official Study Title: Acute Use of Alcohol and Attentional Bias Towards Suicide: An Experimental Test of the Attention-Allocation Model

NCT number: NCT04276779

Date of the document: December 1, 2023

Statistical Design and Power

Statistical Design

Data from Qualtrics (Session 1 baseline data), excel (paper data entered from Session 1 and 2), and DirectRT software will be exported into IBM SPSS statistical software, Version 25. Standard data quality checks and cleaning procedures will be completed. Most notably, any participants voicing awareness of the study aims or not responding adequately to the mood induction will be removed from the initial analyses. Second, manipulation checks will be performed by comparing the participants in the mood conditions on self-reported mood post-manipulation. We expect that negative mood participants will have greater mean scores on the guilt and sadness subscales and lower mean scores on the joviality subscale compared to the positive mood participants.

Study variables for the entire sample will be examined using descriptive statistics such as frequencies and percentages (for categorical variables) and means, standard deviations, and ranges (for continuous variables) to ensure values are reasonable. Prior to conducting analyses related to the hypotheses of the study, individual distributions of continuous variables will be examined visually with histograms to confirm that all assumptions for the analyses are reasonably met. Methods robust to distributional assumptions will be used as appropriate.

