Prior to analysis, Suicide Stroop scores will be evaluated for outliers. We will exclude: trials with incorrect responses, trials with response latencies ± 2 SD from each participant's mean response latency, participants with a mean response latency ± 2 SD from the overall sample's mean, participants whose error rate was +2 SD above the error rate for all participants. We will also examine the reliability, factor structure, and concurrent validity for the suicide-related alcohol expectancies measure (created for this study) prior to its use for Hypothesis 3. We will use exploratory factor analysis (with parallel analysis), Cronbach's alpha, and examine associations with AUDIT total scores and past suicidal ideation severity. Finally, we will confirm there were no pre-existing relevant differences in mood states between our mood and alcohol conditions by estimating measures of association (i.e., R²) between condition assignment and pre-manipulation sad, guilty, and joviality mood states.

Pre-Pilot tests: To finalize study procedures, for the 10 pre-pilot subjects, we will examine prevalence of mood induction effectiveness. If >50% fail the mood induction, we will replace it with another effective mood induction (imaginative film). We will also run frequencies to examine percentage of participants who are successfully deceived, expecting these percentages to be high (>90%). We will use these results to adjust the protocol in order to improve success of our mood manipulation and deception.

Specific Aim 1, Hypothesis 1a: To test the feasibility our experiment, we will first quantify the number of individuals who contact our lab about the study and the percentage who are eligible and participate. We will run descriptive statistics to quantify 1) prevalence of successful mood induction (expecting at least 75%), 2) distress ratings after the study session (expecting average ratings to be low), and 3) number of adverse events (expecting less than 1% of pilot subjects). **Objective 1b:** Using measures of effect size (i.e., Cohen's d, Cramer's V) and t-tests and Chi square analyses, we will examine sociodemographic differences (gender, age, race/ethnicity, income, and alcohol use history) in these feasibility factors.

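### No mood reading is taken between the drink and the mood induction, so an induction-success label based on PANAS-X would mix the effects of both

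*Protocol*

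**What the plan says.** The order of events at Session 2 is clear from the Protocol, Procedures.

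- On arrival, before any drink: "We will assess pre-manipulation mood via the Positive and Negative Affect Schedule-Expanded Form (PANAS-X" (sadness, guilt and joviality subscales).
- Then the drink: "They will proceed first to beverage administration". Twenty minutes are allotted for drinking, followed by breath readings.
- Just before the induction, a brief check: "Participants will rate their level of intoxication on a scale of 0". It contains no mood item.
- After the induction: "After the mood induction, participants will complete the PANAS-X subscales as a manipulation check (<2 min" is the stated duration and purpose. The Stroop task follows. Table 1 agrees, listing "Mood induction (positive or negative); Manipulation check: PANAS-X" on one line.

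The success or failure of the induction in each person is used three times in the SAP. Under Statistical Design, those "not responding adequately to the mood induction will be removed from the initial analyses". Under Hypothesis 1a, a feasibility outcome is "prevalence of successful mood induction (expecting at least 75" percent), with no split by beverage. Under Pre-Pilot tests, more than 50% failures among the 10 pre-pilot subjects leads to a different induction. The Power section assumes one 25% failure rate for every cell. No document says how success or failure is decided.

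**The concern.** In the partial test there was no alcohol, so a change in mood from arrival to after the induction could reasonably be credited to the induction. In this trial a drink comes between the two readings. The Protocol (Alcohol Expectancies) itself allows that drinking can move mood in either direction: people with positive expectancies "who experience positive mood prior to drinking are likely to experience increases in positive mood", while distress often rises when alcohol is taken in a negative mood.

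Suppose success is judged on PANAS-X, either as a post-induction score or as a change from arrival. A participant whose mood the drink has lifted then looks more like a failure of the negative induction, or a success of the positive one. Success rates could differ by beverage arm although the induction works equally well in both.

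No planned analysis would show this. The SAP compares alcohol conditions on mood only before the manipulations, compares mood conditions only after them, and reports success as one pooled prevalence. At stake is the pilot's first aim, feasibility, and what it can tell a later trial about inducing mood under alcohol.

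**Working it through.** **1. The plan's own figures.** With n = 30 per cell, σ = 1 and a 68% multiplier of 0.994 (SAP, Power and Sample Size Considerations):

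- alcohol effect within a mood group: 0.994 × √(2/30) = 0.257 (stated .26)
- interaction: 0.994 × 2/√30 = 0.363 (stated .36)

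Both reproduce. Separately, 150/4 = 37.5 per cell, and 37.5 × 0.75 = 28.1, not 30. That is another matter, but 37.5 is the starting size used below.

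**2. Failure by cell.** Assumptions, none of them given in the documents except the 25%:

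- success is judged on mood change in the intended direction, normal with SD 1;
- the induction works equally well in all cells;
- 25% fail on placebo, so the cut-off is z(.25) = −0.674;
- alcohol lifts mood by δ before the induction, and placebo does not move it.

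Failure is Φ(−0.674 + δ) in alcohol-negative and Φ(−0.674 − δ) in alcohol-positive. Pooled success is 1 minus the mean of the four failure rates. Numbers retained are 37.5 × (1 − failure), against 28.1 in each placebo cell.

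| δ (SD) | Alcohol-negative failure | Alcohol-positive failure | Retained (neg / pos) | Pooled success |
|---|---|---|---|---|
| 0 | 25.0% | 25.0% | 28.1 / 28.1 | 75.0% |
| 0.2 | 31.8% | 19.1% | 25.6 / 30.3 | 74.8% |
| 0.4 | 39.2% | 14.1% | 22.8 / 32.2 | 74.2% |

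Example at δ = 0.2: (0.25 + 0.25 + 0.318 + 0.191)/4 = 0.252, so pooled success is 74.8%. If alcohol lowers mood, the two alcohol cells swap.

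**3. Effect on H3 precision.** Take a larger shift, δ = 0.5, where failure is 43.1% and 12.0% and 21.3 and 33.0 remain. With the 68% multiplier rounded to 1, the interaction half width is √(1/21.3 + 1/33.0 + 2/28.1) = 0.385. With equal 25% failure it is √(4/28.1) = 0.377. The loss is negligible.

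**4. Effect on H3 bias.** Let r be the correlation between mood response and Stroop interference (assumed). With M(c) = φ(c)/(1 − Φ(c)), removing failures shifts the alcohol effect by r × [M(−0.674 + δ) − M(−0.674)] in the negative-mood group. In the positive-mood group the shift is −r × [M(−0.674 − δ) − M(−0.674)].

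- δ = 0.3, r = 0.3: 0.3 × 0.152 = 0.046 and 0.3 × 0.127 = 0.038; difference 0.008 SD.
- δ = 0.5, r = 0.5: 0.5 × 0.267 = 0.133 and 0.5 × 0.196 = 0.098; difference 0.035 SD.

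Both shifts have the same sign, so they largely cancel in the interaction. The simple effects move by less than their stated half width of .26.

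**The case against.** The strongest reply is that the label may not rest on PANAS-X at all. The SAP gives no criterion and plans no change score. The one place where individual failure is traced to a source is the Protocol's Preliminary Data, where 5 participants said in post-study interviews that the induction had not worked. If that route is used, any mixing comes through the participant's own judgement and not through the timing of the scale. This stands, and it is why the point is conditional.

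The size is also unsupported by the documents. The 0.2 to 0.4 SD shift is assumed. The Protocol's remarks on alcohol and mood depend on expectancies and on mood before drinking, so they do not amount to a general statement that alcohol raises or lowers mood. All participants are told they are drinking alcohol, so expectancy could move mood on placebo too and narrow the gap between arms.

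A reader might infer that the trial cannot separate alcohol's effect on mood from its effect on attention. The documents do not support that. PANAS-X is taken after the induction and before the Stroop in both beverage arms, so a randomised comparison already estimates alcohol's effect on mood at the time attention is measured.

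Finally, tabulating failures by cell would expose unequal rates without any new measurement. That is true, but the table would not say whether the drink or the induction caused them.

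**Conclusion.** The gap in the schedule is real. If success is judged on PANAS-X, the person-level label mixes drink and induction, and a pooled rate near 75% can hide failure of 32% to 39% in one alcohol cell and 19% to 14% in the other. Those figures are an illustration resting on the assumptions in the working, not an estimate.

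The consequence is limited. A reader might infer that the manipulation check is invalid or that H3 is materially biased; neither follows. Negative-versus-positive comparisons of post-induction mood within a beverage arm are protected by randomisation. Under a shift common to both mood groups, the bias in the H3 interaction is at most 0.035 SD over the range examined. What the pilot cannot establish is whether an apparent failure under alcohol reflects the induction or a mood shift already present before it. That bears on feasibility and is cheap to repair.

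**What to change.** 1. Repeat the three PANAS-X subscales at the existing check, with the intoxication rating and directly before the induction, in both beverage arms.
2. State the criterion for induction success in the SAP, including whether exit-interview reports count.
3. Report Hypothesis 1a success for each beverage-by-mood cell, using change from the new reading to the post-induction reading.
4. Report the change from arrival to the new reading by beverage arm.
5. Do not adjust alcohol effects for the new reading, because it is taken after the drink. The arrival reading keeps its baseline role.
6. Also report H3 in all randomised participants. The extra reading does not cure the selection caused by removing people on a response measured after randomisation.

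The cost is under 2 minutes per participant by the Protocol's own timing of the scale, on a form already in use, plus short wording changes in both documents. There are three downsides: a third exposure to the scale, which may cue the study aims; a short delay before the induction; and some remaining alcohol effect in the new change score, because BrAC may still be rising during the induction. If sessions have already been run, items 2 and 6 and the breakdown by cell in item 3 still apply, using the readings available.

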Alcohol Expectancies. Likewise, there is limited understanding of individual differences, such as alcohol expectancies, that may further moderate these relations. As has been described in the other-directed aggression literature²⁰, impelling and inhibiting factors may change the effect of AUA on suicide-related attentional bias and thus suicidal behavior. Alcohol expectancies, defined as one's cognitions about the effects of alcohol intoxication²², may inhibit or impel suicidal thoughts and behaviors. First, AUA may facilitate suicidal behavior, in part, by activating suicide-related alcohol expectancies (i.e., increased pain tolerance and fearlessness).² Thus, suicide-related alcohol expectancies may become a salient cue to which attention is directed, thus increasing suicide-related attentional bias. I could find no published studies that have examined suicide-related alcohol expectancies in relation to suicidal thoughts or behaviors. However, my prior work has shown that alcohol use is associated with perceived fearlessness and pain tolerance^{11,23}—constructs theorized to enable someone to attempt suicide, if desired.²⁴ Relatedly, my work has shown that problematic drinking is negatively associated with suicidal ideation among people with low aggressive expectancies.9 Other researchers have similarly shown that beliefs about alcohol reducing fear and pain were associated with increased risk for *nonsuicidal* self-injury.²⁵ Alternative to this expectancy-activation hypothesis is the possibility that individuals drink alcohol purposefully to increase capability for an attempt. However, prior research has shown this is unlikely.²⁶

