Theorists have conjectured that the impact of AUA on suicide risk may depend on alcohol expectancies and increased suicide-related attentional bias. However, for obvious ethical reasons²⁷, no experimental tests of this hypothesis exist. Addressing these challenges, the proposed experiment is an ethical and innovative test of these hypotheses; it examines a construct theorized to occur early in the trajectory towards suicidal behavior but which has not yet been examined in relation to AUA: suicide-related attentional bias.³ This experiment complements NIAAA's strategic goals in basic science and prevention research, as it examines targetable cognitive factors that may influence suicidal ideation—a significant comorbidity among individuals with alcohol use disorders. This study challenges the current paradigm in alcohol-related suicide research in two important ways. First, it represents the first known experimental test of the AAM as it applies to suicide-related attentional bias and would guide methodology and parameters for future related studies, including those with samples higher in dysregulated mood. Further, this would be the first known study of suicide-related expectancies, another frequently hypothesized but untested correlate of alcohol-related suicide risk. If our hypotheses are supported, it would provide empirical support for a larger-scale test of the AAM as is relates to suicide risk. Future laboratory tests could test whether decreasing the salience of negative mood reduces suicide-related attentional bias. If alcohol expectancies are associated with suicide-related attentional bias, future work could test interactive effects of alcohol expectancies with mood and AUA on this bias. Downstream clinical implications include targeting expectancies and negative mood among individuals who consume alcohol. Ultimately, these findings may inform future basic and applied research examining the effects of AUA on suicidal ideation and behavior.

[figure not shown]
Approach

Consistent with theoretical and empirical work regarding the effects of AUA on suicidal thoughts and behaviors, this pilot study will test the interactive effects of Figure 2. Summary of Research Approach

AUA, negative mood, and alcohol expectancies on suicide-related attentional bias. The proposed study will employ a 2x2, between subjects design (alcohol-placebo X negative mood-positive mood, baseline levels of expectancies). See Figure 2 for a summary of our approach.

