Specific Aim 4, Hypothesis 4: Explore the conditional effect of AUA on suicide-related attentional bias by alcohol expectancies. The relation of suicide-related alcohol expectancies with suicide-related attentional bias will be stronger among those in the AUA condition compared to those in the placebo condition.

Analysis: The interactive effect of expectancies and alcohol (Alcohol X Expectancies) on attentional bias towards suicide-related cues (Stroop interference score, calculated by subtracting the response latencies for neutral words from the latencies for suicide-related words) will be estimated using a general linear model of the form $\hat{Y} = \beta_0 + \beta_1 Alcohol + \beta_2 Expectancies + \beta_3 Alcohol \times Expectancies$, where \hat{Y} is the average Stroop

interference score, *Alcohol* is a binary indicator (1=yes, 0=no) of assignment to alcoholic beverage intake, and *Expectancies* is a continuous score of alcohol expectancies (higher scores indicate higher expectancies). The coefficient β_2 estimates the differential effect of expectancies conditional on alcohol intake. With the model, we

will estimate Stroop inference scores by alcohol conditions at the mean expectancy and ± 1 SD away from the mean, expecting that in the alcohol condition, expectancies will have a stronger association with attentional bias towards suicide scores. Measures of effect size (e.g. R², partial eta², Cohen's r) will be used to aid in interpretation. Inferences will be conducted using confidence intervals for the comparisons of interest.

Power and Sample Size Considerations

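### H4's Alcohol × Expectancies term cannot show an expectancy association shared by both beverage arms, and the average slope that the protocol says needs testing is not pre-specified

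*Protocol*

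**What the plan says.** **Instruction and cues.** Protocol, Procedures (Manipulation of AUA and Mood): "We will tell all participants that they are drinking alcohol". Placebo drinks contain a small amount of alcohol in and on the juice, and "the rims of the glasses will be sprayed with alcohol just prior to being served".

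**Design.** Protocol, Approach: a "2x2, between subjects design (alcohol-placebo X negative mood-positive mood, baseline levels of expectancies"). There are two beverage arms, and neither is told that it is not drinking alcohol.

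**Mechanism.** Protocol, Theoretical Framework (Alcohol Expectancies): "First, AUA may facilitate suicidal behavior, in part, by activating suicide-related alcohol expectancies". The same section says that these expectancies may then become a salient cue that draws attention.

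**What needs testing.** The same section ends: "there remains a need to test the main effects of alcohol expectancies on suicide-related attentional bias". Protocol, Innovation, adds that if expectancies turn out to be associated with the bias, "future work could test interactive effects of alcohol expectancies with mood and AUA on this bias". The Proposed Study section, however, describes the pilot as examining an interactive impact.

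**H4.** SAP, Specific Aim 4: the relation between suicide-related expectancies and the bias "will be stronger among those in the AUA condition compared to those in the placebo condition". The model is Ŷ = β0 + β1 Alcohol + β2 Expectancies + β3 Alcohol × Expectancies, with Alcohol coded 1/0 and expectancies continuous. The SAP identifies β2 as the differential effect. The planned output is predicted scores by arm at the mean expectancy and one SD either side. The protocol's Analytic plan promises linear contrasts for H3 and H4 but lists none for H4.

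**The concern.** The placebo is built so that both arms believe they have drunk. If belief alone brings a person's expectancies into play, some or all of the expectancy slope will appear in the placebo arm as well, and H4's only named comparison, the difference between the arms' slopes, removes that shared part.

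The protocol's background puts the question the other way round: first whether expectancies relate to the bias at all, then whether that relation depends on alcohol and mood. H4 goes straight to the second step and gives no named estimate or interval for the first.

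The coefficient label adds to the risk. If the slopes are similar and nonzero, someone following the SAP's text would report β2, the placebo slope, as moderation by alcohol. Someone using β3 would see little and might conclude that expectancies do not matter. Neither would report the association on which the protocol bases its next study.

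**Working it through.** **1. The plan's own precision figures (H3).** Inputs from SAP, Power and Sample Size Considerations: n = 30 per cell, σ = 1, 68% intervals; z(.84) = .9945.
- Alcohol effect within a mood group: SE = √(2/30) = .258; half-width = .9945 × .258 = .257 (stated .26).
- Alcohol × Mood: SE = 2/√30 = .365; half-width = .363 (stated .36).
- Detectable at 80% power, two-sided .05: 2.802 × .258 = .723 and 2.802 × .365 = 1.023 (stated .72 and 1).

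These reproduce. The SAP gives no such figure for H4.

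**2. What the H4 coefficients are.** Set Alcohol to 0 and then to 1:
- placebo slope = β2
- alcohol slope = β2 + β3
- difference = β3
- average = [β2 + (β2 + β3)]/2 = β2 + β3/2

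If the placebo slope is c and the alcohol slope is c + d, then β3 = d and the average is c + d/2. The shared part c is absent from β3 whatever its size. A simulation with slope .30 in both arms, 60 per arm, gave a mean β3 of −.002 and a mean average slope of .301.

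**3. Precision for H4.** Inputs: 30 per cell × 2 mood cells = 60 per beverage arm. Assumption: expectancy score standardised and residual SD 1.

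| Estimate | SE | 68% half-width |
|---|---|---|
| One arm's slope | 1/√60 = .129 | .13 |
| β3 | √(1/60 + 1/60) = .183 | .18 |
| β2 + β3/2 | ½√(1/60 + 1/60) = .091 | .09 |

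The two arms' slopes come from different people, so the variance of the average is one quarter of the variance of the difference, and the ratio of two in SE holds at any sample size. Removing 25% of 150 leaves 112.5, not 120. At N = 112 the SEs are .189 and .094, and the reading is unchanged.

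**4. Illustration.** Neither input below is in the documents. Take an alcohol-arm slope b = .30 and let the placebo arm carry a fraction f of it, so that β3 = (1 − f)b and the average = (1 + f)b/2. Power is two-sided .05.

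| f | β3 | Power | Average slope | Power |
|---|---|---|---|---|
| 0 | .30 | 38% | .15 | 38% |
| .5 | .15 | 13% | .225 | 69% |
| 1 | 0 | 5% | .30 | 91% |

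At f = .5, with b running from .2 to .5, power is 8.5% to 27.8% for β3 and 37.6% to 98.4% for the average slope. At f = 0 the two are equal. Power serves here only as a scale; the plan infers from intervals.

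**The case against.** **H4 is a coherent test as it stands.** The attention-allocation model says that intoxication narrows attention to salient cues. If expectancies are such a cue, a steeper slope under alcohol is what it predicts, and equal belief across arms is a deliberate control. This stands: β3 should stay, described as what alcohol adds.

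**The arm slopes are already visible.** Predicted scores by arm at the mean and ±1 SD would show two parallel, nonzero slopes if that is what the data hold. The plan is exploratory and has no rule that turns a small β3 into evidence against expectancies. This largely stands. The average slope can be computed from the planned fit and is merely not named, so the gap is one of pre-specification.

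**The main-effect sentence closes a literature review.** The next section announces an interactive test, so the sentence is not a promised estimand. That is fair, but the Innovation section also makes later interaction work conditional on an association, and the plan names no overall estimate of one.

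**The average slope does not identify activation.** Expectancies are measured at Session 1 and not randomised. In the protocol's preliminary sample the suicide-related score correlated with past-year ideation (r = .43) and differed by hazardous drinking (d = .52). A nonzero average slope could arise with no activation at all. This stands and limits what the added estimate can be said to show. Its smaller SE is no argument that it answers H4's question better.

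**Conclusion.** The concern holds as a gap in pre-specification and interpretation. β3 removes any expectancy association common to the two arms, and the average slope that would answer the protocol's main-effect question is not named. The SAP's description of β2 is wrong under its own coding. At 60 per arm, with standardised scores and residual SD 1, the SE is about .18 for β3 and .09 for the average slope.

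Three stronger readings are not supported.
- A reader might infer that the placebo activates expectancies as fully as alcohol does, so that β3 must be near zero. Activation is not measured, and the alcohol arm also has real intoxication cues at a BrAC of about .08%. Partial activation would dilute β3 without abolishing it.
- A reader might take the SAP's expectation of more than 90% successful deception as a placebo belief rate and compute how much of the effect β3 keeps. That figure concerns the 10 pre-pilot subjects and does not separate belief in the beverage from blindness to the study aims; the debriefing section lists both as deceptions. Any such calculation would be pure assumption.
- A reader might conclude that H4 is invalid. It is a valid test of alcohol's added effect.

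**What to change.** In SAP, Specific Aim 4:

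1. Name the average expectancy slope (β2 + β3/2, or the expectancy coefficient with Alcohol coded ±½) and both arm slopes, each with a 68% interval, beside β3.
2. Correct the text: β2 is the placebo-arm slope and β3 is the differential effect.
3. State that β3 tests what alcohol adds among people who were all told they drank, so a near-zero β3 alone is not evidence that expectancies are unrelated to the bias.
4. Describe placebo belief from the post-study interview, which already covers deception failures, and from the 0–11 intoxication rating. The rating's timing is tied to a BrAC threshold, so state when placebo participants give it.

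The cost is some SAP wording and linear contrasts from a model already planned, with no new participants or measures. The downside is one more estimate to report, which must be described as an observational association with a baseline trait and not as evidence of activation.
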